4.1.10 Adverse Event

4.1.10.1 Definition of an Adverse Event

An AE is any untoward medical occurrence in a clinical investigation subject administered an investigational product and which does not necessarily have to have a causal relationship with this treatment.

The analysis of AEs will be based on the principle of treatment emergence. Treatment-emergent AEs (TEAEs) will be defined as events that occur (or worsen) on or after the first treatment date of the study drug

In this study, Pregnancy is an outcome, and not an AE.

4.1.10.2 Definition of a Serious Adverse Event

A serious adverse event (SAE) is any AE occurring within the timelines specified in the protocol that results in any of the following outcomes:

- Death;
- Life-threatening situation (subject is at immediate risk of death);
- Inpatient hospitalization or prolongation of existing hospitalization;
- Persistent or significant disability/incapacity;
- Congenital anomaly/birth defect in the offspring of a subject who received study drug; or
- Important medical events that may not result in death, be immediately life threatening, or require hospitalization, may be considered an SAE when, based upon appropriate medical judgment, they may jeopardize the subject and may require medical or surgical intervention to prevent one of the outcomes listed in this definition.

4.1.10.3 Adverse Events of Specific Interest

Adverse events of particular clinical importance, other than SAEs will be classified as AEs of specific interest (AESIs). For this study, AESIs refer to reports of insertion pain assessed immediately after insertion, pelvic infection (PID or endometritis), expulsion, and uterine perforation. AESIs will be identified and assessed by the Medical Monitor during the ongoing monitoring of safety data during the trial, during DMSB meetings, and for the Clinical Study Report. For each AESI a narrative may be written and included in the Clinical Study Report.

4.1.10.4 Adverse Event Relationship to Study Treatment

The relationship of an AE to the drug will be assigned as one of following relationships:

Not related, unlikely related, possibly related, probably related, and related.

For analysis purposes, "possibly related," "probably related," and "related" to an investigational medical product are considered adverse reactions and will be reported as "Related."

"Unlikely" and "not related" do not qualify as a causal relationship and will be reported as "unrelated".

A missing relationship will be imputed as "related".

4.1.10.5 Adverse Events Related to Study Procedures

Adverse events that occur during the study drug placement procedure or removal procedure will be reported on the AE electronic case report form (eCRF) with a causality assessment of "related to study drug placement procedure."

A missing relationship will be imputed as "related to study drug placement procedure."

4.1.10.6 Adverse Event Severity

The investigator will assess the severity of the AE and severity is one of the following 4 values: Mild, Moderate, Severe, or Life-threatening.

For analysis purpose, Life-threatening will be coded as severe; missing severity will be imputed as severe.

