15.5 Serious Adverse Event and Adverse Event Severity

The investigator will assess the severity of the AE using the following general guidelines:

Mild: An AE that is usually transient, requiring no special treatment, and does not interfere with the subject's daily activities.

Moderate: An AE that introduces a low level of inconvenience or concern to the subject and may interfere with daily activities but is usually ameliorated by simple therapeutic measures.

Severe: An AE that interrupts a subject's usually daily activity and typically requires systemic drug therapy or other treatment (a severe AE may not necessarily qualify as an SAE).

Life-threatening: An AE that put the subject at immediate risk of death from the event as it occurred. This does not include an event that might have led to death if it had occurred with greater severity.

Fatal: An AE that was the cause of the subject's death.

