20.7.3 Safety and Tolerability

The following safety and tolerability analyses will be performed:

- Incidence of AEs and SAEs will be summarized for the ITT population as well as for the Safety populations for all subjects and the 36 to 45-year-old safety subpopulation. The number and percentage of subjects with each AE and SAE will be presented in a table by MedDRA system-organ class and preferred term. Summaries will be presented by relationship to VeraCept and/or VeraCept placement or removal procedure and the severity of the adverse event. All AEs will be summarized, including these AESIs:
 - Pain during insertion
 - Pelvic infection (PID or endometritis)
 - Expulsion
 - Uterine perforation
 - Dysmenorrhea
 - Abdominal pain
- Bleeding and spotting patterns will be summarized (per Mishell [12]) for the ECYC population for the first year of treatment by the number of days in each 28-day cycle with bleeding or spotting, bleeding only and spotting only.
- The insertion pain assessed immediately after insertion will be summarized...
- Cumulative VeraCept continuation rates for Years 1 through 8 will be summarized using Kaplan-Meier methods for the Safety population. The number and percentage of subjects with each reason for discontinuation will be summarized.
- Cumulative VeraCept expulsion rates at for Years 1 through 8 will be summarized using Kaplan-Meier methods for the Safety population.

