4.12.2 Adverse Events by System Organ Class and Preferred Term

The incidence of AEs and SAE will be summarized by MedDRA primary SOC and PT. The summary will include the total number and percentage of subjects reporting an AE within an SOC and/or PT.

The incidence of AEs by SOC and PT for the Safety and ITT populations

The incidence of AEs by SOC and PT by maximum severity for the Safety population

The incidence of AEs by SOC and PT by closest relationship to study drug use for the Safety population

The incidence of AEs by SOC and PT by closest relationship to drug placement/removal procedure for the Safety and ITT populations

The incidence of SAEs by SOC and PT for the Safety and ITT populations

The incidence of SAEs by SOC and PT by maximum severity for the Safety population

The incidence of SAEs by SOC and PT by closest relationship to study drug use for the Safety population

The incidence of SAEs by SOC and PT by closest relationship to drug placement/removal procedure for the Safety and ITT populations

The incidence of AE leading to study drug removal by SOC and PT for the Safety population

The incidence of AE leading to study discontinuation by SOC and PT for the Safety population

Listing of AE leading to death for the ITT population

Incidence of AEs experienced by at least 5% of subjects by SOC and PT for the Safety population

Incidence of AESIs(e.g. pain during insertion, pelvic inflammatory disease, ectopic pregnancies, uterine perforations, expulsions, uterine perforation, dysmenorrhea, and abdominal pain) will be summarized for Safety and ITT populations.

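### The protocol grades AE severity on five levels, but the SAP lists four, has no rule for a Fatal grade and analyses three, so no planned table counts women with a life-threatening event

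*SAP*

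**What the plan says.** Protocol section 15.5 asks the investigator to grade each event on a five-level scale. The top three levels are separately defined:

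- "Severe: An AE that interrupts a subject's usually daily activity and typically requires systemic drug therapy or other treatment". The same entry adds that such an event need not be an SAE.
- "Life-threatening: An AE that put the subject at immediate risk of death from the event as it occurred".
- "Fatal: An AE that was the cause of the subject's death".

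Protocol section 20.7.3 then commits to displaying severity: "Summaries will be presented by relationship to VeraCept and/or VeraCept placement or removal procedure and the severity of the adverse event".

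SAP section 4.1.10.6 describes the same variable differently: "severity is one of the following 4 values: Mild, Moderate, Severe, or Life-threatening". Its next sentence sets the analysis rule: "For analysis purpose, Life-threatening will be coded as severe; missing severity will be imputed as severe".

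Two tables in SAP section 4.12.2 use the result: "The incidence of AEs by SOC and PT by maximum severity for the Safety population" and "The incidence of SAEs by SOC and PT by maximum severity for the Safety population".

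**The concern.** There are two separate problems.

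The first is a value without a rule. An investigator who follows the protocol can record an event as Fatal. The SAP does not list that value and does not say how to handle it, so its place in a maximum-severity table is left to the programmer.

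The second is a loss of information at the top of the scale. The protocol separates an event that interrupts daily activity from one that puts the woman at immediate risk of death. The SAP merges them and adds records with no severity grade. A reader of the severe category cannot tell these three groups apart.

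This matters for this product because protocol section 6.2 lists rare but grave events reported in under 2% of pooled subjects. They include ruptured ectopic pregnancy, uterine hemorrhage with anemia that may need transfusion, and pelvic infection that can lead to sepsis. For events of this kind, the number of women whose life was threatened is a natural safety figure to report.

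**Working it through.** No figure in the plan needs reproducing. The check sets the two scales side by side and then traces where each grade appears in the planned output.

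**Step 1: the scales.**

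| Grade | Protocol 15.5 | SAP 4.1.10.6, as collected | SAP 4.1.10.6, as analysed |
|---|---|---|---|
| Mild | yes | yes | Mild |
| Moderate | yes | yes | Moderate |
| Severe | yes | yes | Severe |
| Life-threatening | yes | yes | coded as Severe |
| Fatal | yes | not listed | no rule |
| Missing | – | – | imputed as Severe |
| Number of levels | 5 | 4 | 3 |

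**Step 2: where a life-threatening event appears.**

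- Brief AE summary (SAP 4.12.1): there are rows for AEs, SAEs, related events, events leading to removal or discontinuation, and death. There is no life-threatening row.
- Maximum-severity tables (SAP 4.12.2): the event is counted as severe.
- SAE tables (SAP 4.12.2): the event is included, because immediate risk of death is one of the seriousness criteria (protocol 15.1, SAP 4.1.10.2). No table splits SAEs by criterion.
- Listings (SAP 4.12.4): severity is a listed field. The SAP does not say whether the collected or the recoded grade is shown.
- Narratives (SAP 4.12.3): SAEs are covered.

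The planned tables therefore give only an upper bound. Leaving aside events graded Fatal, the number of women with a life-threatening event lies between zero and the number in the severe category of the SAE table.

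**Step 3: where a fatal event appears.** Deaths have their own row in the brief summary for the ITT and Safety populations (4.12.1). AEs leading to death are listed (4.12.2, 4.12.4) and deaths are narrated (4.12.3). The protocol also records Fatal as an AE outcome (15.6), and the AE listing includes outcome. What is missing is only the rule for Fatal as a severity grade.

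**Step 4: what the missing count would say.** The documents give no number of life-threatening events, so the counts below are assumptions. The denominator is the planned enrollment of 1,605; the Safety population would be somewhat smaller. The upper limits are exact two-sided 95% (Clopper-Pearson). For zero events the formula is 1 − 0.025^(1/1605) = 0.230%.

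| Assumed women with an event | Rate (x / 1,605) | Upper 95% limit |
|---|---|---|
| 0 | 0% | 0.230% |
| 1 | 0.062% | 0.347% |
| 3 | 0.187% | 0.545% |
| 5 | 0.312% | 0.725% |

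None of these rows could be read off the planned tables. The rows show what a displayed count would allow a reader to state; they are not a forecast.

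**The case against.** The case for leaving the SAP alone has real force.

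- **Deaths are counted.** A reader might infer that the number of women who died is lost. Step 3 shows that it is not.
- **Different events stay apart.** A reader might infer that a ruptured ectopic pregnancy would share a row with severe cramping. The tables are by system organ class and preferred term, so different preferred terms have separate lines. Ectopic pregnancy is also named in the SAP's summary of events of special interest. Grades merge only within a preferred term and in the totals above it.
- **The events are not discarded.** A life-threatening event is an SAE, so it stays in the SAE totals, listings and narratives. The recoding is for analysis, and nothing says that the collected value is deleted.
- **The severe category is not wrong in itself.** A life-threatening event is at least severe, so the category can be read as severe or worse. Imputing missing severity as severe is a defensible worst case and matches the SAP's rule for a missing relationship.
- **The protocol does not promise five displayed levels.** Section 20.7.3 commits only to summaries by severity, which the SAP provides.
- **The Phase 2 SAE figure does not size the problem.** Ten women had SAEs; over 283 that scales to 10/283 × 1,605 ≈ 57 women. This says nothing about how many events would be life-threatening.
- **The SAP is older than the protocol supplied.** It cites protocol version 3.0, and the protocol is now version 7.0. The version 3.0 scale is not available, so the mismatch may be a choice or simply an SAP that was not updated.

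All of this stands, and it limits the harm. It does not supply a rule for a Fatal grade or a table that counts life-threatening events.

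**Conclusion.** The point holds as a small alignment issue. The severity scale has five levels in the protocol, four in the SAP as collected and three as analysed. The SAP has no rule for Fatal, and its severe category pools severe, life-threatening and unrated events. As a result, no planned table reports how many women had a life-threatening event.

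The size in women cannot be stated, because the documents give neither a number nor a share of life-threatening events. The finding concerns safety reporting only; the Pearl Index and the other efficacy analyses do not use severity. It rests on the current protocol and the SAP as supplied, and on the tables named in SAP 4.12. A later SAP or detailed table shells might already separate the grades.

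**What to change.** - In SAP 4.1.10.6, list the five grades of protocol 15.5 and remove the recoding of life-threatening as severe.
- In the AE and SAE maximum-severity tables of SAP 4.12.2, show life-threatening and fatal as separate levels. A combined severe-or-worse row can be kept. A lighter alternative is a life-threatening row in the brief AE summary of SAP 4.12.1; a rule for Fatal in 4.1.10.6 is needed either way.
- Keep the imputation of missing severity as severe, and footnote the number of records imputed in each table.
- State in SAP 4.12.4 that the listing shows severity as collected.

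The cost is SAP wording and at most two extra rows in two table shells, plus a footnote. Protocol 15.5 already requires the grades, so no new data are needed. The SAP also still describes a five-year study while the protocol runs to eight, so the change can go into the same update.

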4.1.11 Imputing Missing or Incomplete Dates of Adverse Events and Concomitant Medications

The most conservative approach will be systematically considered. If the AE onset date is missing / incomplete, it is assumed to have occurred during the study treatment phase (i.e., considered a TEAE) except if the partial onset date or other data such as the stop date indicates differently. Similarly, a medication with partial start and stop dates could be considered as both a prior and concomitant treatment.

The following algorithms will be applied to missing and incomplete start and stop dates:

Start Dates

- If the day portion of the start date is missing, then the start date will be estimated to be equal to the date of first insertion, provided the start month and year are the same as the first insertion and the stop date is either after the first insertion or completely missing. Otherwise, the missing day portion will be estimated as "01."
- If both the day and month portions of the start date are missing, then the start date will be estimated to be equal to the date of first insertion, provided the start year is the same as the first insertion and the stop date is either after the first insertion or completely missing. Otherwise, the event will be assumed to start on the first day of the given year (e.g., ??-???-2013 is estimated as 01-JAN-2013).
- If the start date is completely missing and the stop date is either after the first insertion or completely missing, the start date will be estimated to be the day of first insertion. Otherwise, the start date will be estimated to be the first day of the same year as the stop date. All other non-AE and non-concomitant medication day calculations where only partial dates are available will be handled as follows: the first day of the month will be used in the calculations if the day part of a start date is missing while January 1 will be employed if both the month and day parts of a start date are missing.

Stop Dates

- If only the day of resolution is unknown, the day will be assumed to be the last of the month (e.g., ??-JAN-2013 will be treated as 31-JAN-2013).
- If both the day and month of resolution are unknown, the event will be assumed to have ceased on the last day of the year (e.g., ??-???-2013 will be treated as 31-DEC-2013).
- If the stop date is completely missing or the event is continuing, the event will be assumed to be after first insertion and will be imputed using the last known date on the study.

4.2 Analysis Populations

4.2.1 Analysis Populations

• ITT

All subjects who underwent the study drug placement procedure, regardless of whether the study drug was successfully placed or not.

• Safety:

ITT subjects who had the study drug successfully placed

• Safety Subgroup (36-45 years):

Subjects in the Safety population who were between 36 to 45 years of age (inclusive) at enrollment.

• Evaluable for Pregnancy (EP):

ITT subjects who had VeraCept placed successfully and meet requirements 1, 2 and 3 as follows. Subjects must also meet either requirement 4 or requirement 5 to be part of the EP study population:

- 1. Be post-menarcheal up to 35 years of age (inclusive) at enrollment
- 2. Have at least one report of pregnancy status after being enrolled
- 3. Do not have pre-treatment pregnancy, which is defined as the estimated conception date being before the insertion date.

AND

4. Have at least 1 cycle of e-diary with intercourse and without any backup contraception or emergency contraception

OR

5. Have an on-treatment pregnancy, which is defined as the estimated conception date being on or after the insertion date and no more than 7 days after the VeraCept is removed or expelled.

Subjects with major protocol violations that are deemed to have had a material impact on the primary efficacy assessment will be excluded from EP analysis population. Exclusions based on major protocol deviations will be reviewed and approved by the Sebela and its designee.

• Evaluable for Cycle Control (ECYC):

ITT subjects with at least one cycle for which:

1. A pregnancy did not occur;

AND

2. There was an assessment of bleeding reported by the subject.

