20.1 Analysis Populations

The following analysis populations will be created:

• Intent to Treat (ITT):

All subjects who underwent the study drug placement procedure, regardless of whether the study drug was successfully placed or not.

• Safety:

ITT subjects who had the study drug successfully placed

• Safety Subgroup (36-45 years):

Subjects in the safety population who were between 36 to 45 years of age (inclusive) at enrollment.

• Evaluable for Pregnancy (EP):

ITT subjects who had VeraCept placed successfully and meet requirements 1, 2 and 3 below. Subjects must also meet either requirement 4 or requirement 5 to be part of the EP study population:

- 1. Be post-menarcheal up to 35 years of age (inclusive) at enrollment
- 2. Have at least one report of pregnancy status after being enrolled
- 3. Do not have pre-treatment pregnancy, which is defined as the estimated conception date being before the insertion date.

AND

4. Have at least 1 cycle of e-diary with intercourse and without any backup contraception or emergency contraception (EC)

OR

5. Have an on-treatment pregnancy, which is defined as the estimated conception date being on or after the insertion date and no more than 7 days after the VeraCept is removed or expelled.

Subjects with major protocol violations that are deemed to have had a material impact on the primary efficacy assessment will be excluded from EP analysis population. Exclusions based on major protocol deviations will be reviewed and approved by Sebela and its designee.

• Evaluable for Cycle Control (ECYC):

ITT VeraCept subjects with at least one cycle for which:

1. A pregnancy did not occur;

AND

2. There was an assessment of bleeding reported by the subject.

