3 STUDY DESIGN AND INVESTIGATIONAL PLAN

This study is a prospective, multi-center, single-arm, open-label, Phase 3 clinical study to 3 years with an extension up to 5 years.

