4.9 Primary Endpoint Analysis

The primary efficacy endpoint is contraceptive efficacy through 3 years of use and will be analyzed using the Pearl Index with a 95% CI (CI) for women in the EP population.

The Pearl Index is defined as the number of on-treatment pregnancies per 100 women years. On-treatment pregnancy is defined as the estimated conception date being after the insertion date and no more than 7 days after the VeraCept is removed or expelled. One woman year is defined as comprising thirteen 28-day cycles.

Point estimate of Pearl Index:
$$x \times \frac{1300}{E}$$

95% CI: $\left(\frac{1}{2}\chi_{(0.025,2x)}^2 \times \frac{1300}{E}, \frac{1}{2}\chi_{(0.975,2(x+1))}^2 \times \frac{1300}{E}\right)$

where x is the number of on-treatment pregnancies and E is the number of 28-day evaluable exposure cycles and $\chi^2_{(p,df)}$ is the pth quantile of χ^2 -distribution with df degrees of freedom.

Cycles during which no intercourse occurs or backup methods of contraception (including emergency contraception) are used or there is no diary data will be excluded from the primary analysis of the Pearl Index unless the subject had an on-treatment pregnancy in that cycle. If Cycle 1 is evaluable, it will be included in the analysis regardless of the timing of VeraCept relative to the subject's last pre-insertion menses.

x =sum of PREGNANCY

E =number of Evaluable Cycles (NCYCEV)

Pearl Index point estimate and 95% CI will be calculated for Year 1, Year 2, and Year 3, separately, and for 3 years cumulatively.

The analysis will be repeated for the following subgroups

- Race (white, non-white)
- BMI group at enrollment
- Age group at enrollment
- Parity at enrollment

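### Deviation exclusions from the primary EP set are judged without stated masking to pregnancy or a decision time, and no planned analysis shows their effect on the Pearl Index

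*SAP*

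**What the plan says.** SAP 4.9 states that the primary endpoint "will be analyzed using the Pearl Index with a 95% CI (CI) for women in the EP population". The numerator is "x =sum of PREGNANCY", taken over the women in that set.

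To be in EP, a woman up to 35 must have had a successful placement and meet requirements 1 to 3. She must also meet either requirement 4 (at least one diary cycle with intercourse and no backup method) or requirement 5: "Have an on-treatment pregnancy, which is defined as the estimated conception date being on or after the insertion date" and no later than 7 days after removal or expulsion.

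After these requirements SAP 4.2.1 adds a subject-level exclusion: "Subjects with major protocol violations that are deemed to have had a material impact on the primary efficacy assessment will be excluded" from EP. On who decides, it says: "Exclusions based on major protocol deviations will be reviewed and approved by the Sebela and its designee". Protocol 20.1 has the same rule ("Exclusions based on major protocol deviations will be reviewed and approved by Sebela and its designee"), as does the protocol synopsis under Statistical Methods.

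The cycle-level rule is drafted differently. SAP 4.9 says that cycles with no intercourse, backup contraception or no diary data "will be excluded from the primary analysis of the Pearl Index unless the subject had an on-treatment pregnancy in that cycle". The subject-level rule contains no comparable provision.

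Protocol 18 requires immediate reporting of confirmed or suspected pregnancies to the sponsor. Protocol 6.4 adds a monthly safety and pregnancy review with the study principal investigator. The trial is single-arm and open-label.

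**The concern.** The test for exclusion is whether a violation materially affected the efficacy assessment. In a trial whose efficacy outcome is pregnancy, that is hard to judge apart from whether the woman conceived. The organisation that approves exclusions also receives every pregnancy report. Neither document says that the decision is made before lock, from a fixed list, or without sight of pregnancy status.

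The judgement matters mainly for women who conceived. Cycles with backup contraception, no intercourse or no diary data are already removed by rule, so excluding a woman who did not conceive takes out a little exposure and hardly moves the index. Excluding a woman who did conceive takes out one of a small number of events. If such exclusions were related to outcome, the Pearl Index and its upper confidence limit would be biased downward, and those are the figures intended to support filing. The only efficacy sensitivity analysis (SAP 4.10.1) puts back excluded cycles in the Kaplan-Meier analysis; it does not put back excluded women.

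**Working it through.** **Inputs**
- Year 3 evaluable exposure: 577 woman-years (SAP 3.7; Protocol 20.9).
- Precision target: upper 95% limit no more than 1 unit above the point estimate (same sections).
- Interval: exact Poisson (SAP 4.9). Per 100 woman-years W, index = 100x/W and upper limit = 100 × ½χ²(0.975, 2(x+1))/W.
- Year 1 exposure: over 17,000 cycles from 1,605 women, of whom 1,480 are up to 35 (SAP 3.7).
- Pregnancy counts x are illustrative. The documents state no assumed Pearl Index.

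**The plan's own figure**

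For x = 3, ½χ²(0.975, 8) = 8.767. The distance from point estimate to upper limit is (8.767 − 3) × 100/577 = 0.9995. The smallest W giving a distance of at most 1 is 576.7, which rounds up to 577. The planned figure is therefore reproduced if 3 pregnancies in Year 3 (index 0.52) were assumed. That assumption is inferred; 0.52 also happens to be the one-year Phase 2 Pearl Index in Protocol 1.1.3.

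**One excluded pregnancy in Year 3 (577 woman-years, exposure otherwise unchanged)**

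| x | Index | Upper limit | Distance |
|---|---|---|---|
| 5 | 0.87 | 2.02 | 1.16 |
| 4 | 0.69 | 1.77 | 1.08 |
| 3 | 0.52 | 1.52 | 0.9995 |

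Each step lowers the index by 100/577 = 0.17. The upper limit falls by about 0.25 at each of these steps. Going from 4 to 3 also takes the distance from above to just below the 1-unit target. That crossing is fragile: if one full woman-year leaves with the excluded woman, W is 576 and the distance is 1.001.

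**Excluding women who did not conceive**

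Taking 10 woman-years out at x = 5 moves the index from 500/577 = 0.867 to 500/567 = 0.882.

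**Three years cumulatively**

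The documents do not give this exposure, so a range is assumed.
- Low: 3 × 577 = 1,731 woman-years, which treats Years 1 and 2 as no larger than Year 3.
- High: 17,000/13 = 1,308 woman-years in Year 1; pro rata for women up to 35, 1,308 × 1,480/1,605 = 1,206. Using that for both Years 1 and 2 gives 1,206 + 1,206 + 577 = 2,989.

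One pregnancy is then worth 100/1,731 = 0.058 down to 100/2,989 = 0.033. For example, going from 10 to 9 pregnancies moves the upper limit from 1.06 to 0.99 at 1,731 woman-years, and from 0.62 to 0.57 at 2,989.

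**The case against.** Four points on the other side have force.

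**The plan is transparent about exclusions.** A reader might infer that a removed pregnancy would go unseen. The documents do not support that. SAP 4.5 requires a listing of each woman's population membership with the reason for any exclusion, SAP 4.6 tabulates and lists deviations, and Protocol 19.3 has all deviations recorded on the eCRF. A removed pregnancy could be found and added back by hand. What is missing is a planned re-estimate.

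**A deviation process exists.** Protocol 16 says deviations are reviewed under a process set before the first patient was enrolled. That process is not in these documents and may define major violations, timing or access to outcomes. This stands as a limit: the gap is in what the protocol and SAP state. Protocol 16 itself does not mention EP exclusions or masking.

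**Use of pregnancy status is an inference.** A reader might conclude that the sponsor decides in knowledge of the outcome, or that a pregnancy has been dropped. The documents show only that the sponsor receives pregnancy reports and that nothing stated keeps that information out of the decision. Nothing shows that it is used or that any pregnancy was removed.

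**Requirement 5 is not a blanket guarantee.** It is an alternative to requirement 4, and successful placement and requirements 1 to 3 still apply. The point therefore concerns pregnancies that already qualify for EP.

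It is also fair that no success threshold for the Pearl Index is stated, so no formal pass or fail turns on one exclusion.

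**Conclusion.** The point holds as a gap in safeguards. Both documents permit a judgement-based exclusion from the primary set, with no stated list, masking or decision time, and it can take a qualifying on-treatment pregnancy out of the numerator. The exclusion would be listed, but its effect on the estimate would not be shown.

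The effect is clear in a single year, where the Year 3 index falls by about a quarter when one of four pregnancies is excluded (0.69 to 0.52). It is modest over three years. The size rests on illustrative pregnancy counts, on the planned 577 woman-years being achieved and, for the cumulative figure, on the assumed exposure range. What is affected is the estimate, its interval and the 1-unit precision target.

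**What to change.** Make the change in SAP 4.2.1 and in the matching protocol text (20.1 and the synopsis), so that the two documents stay aligned.

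1. Decide EP deviation exclusions before database lock, by people masked to pregnancy status, from a pre-specified list of violations applied identically to women who did and did not conceive. A rule that spared only pregnant violators would keep the events while dropping other violators' exposure, and would bias the index upward. Refer to the deviation process in Protocol 16 if it already contains this. Apply the change to each analysis not yet locked: Protocol 6.2 already reports pooled adverse events through 3 years that include this trial, so the 3-year analysis may be past that stage.
2. In SAP 4.9, add a sensitivity Pearl Index with 95% CI in all successfully placed women who meet EP requirements 1 to 3 and either 4 or 5, with no deviation exclusions. This can be done whether or not the masked review is still possible.

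The cost is wording in two documents and one repeated table. The sensitivity index may be slightly less favourable than the primary one.
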